#### **8.5 Stool Data and Results**

Number of formed and unformed bowel episodes will be listed per subject by treatment group and time on randomized population.

The number of subjects will be distributed to the corresponding frequency of formed and unformed bowel episodes by treatment group. The percentage will be calculated based on safety population.

Stool Culture Results of E.coli (ETEC & EAEC), Other Microorganism (example: Campylobacter, Salmonella, Shigella), Stool microscopy for ova and parasites will be summarized on the values of present or absent by treatment in Day 1 and TOC visits on mITT & Per-Protocol Population.

#### **8.6 Protocol deviations**

The following describes the protocol deviations that relate to statistical analyses or Per-protocol population.

All deviations related to study inclusion and exclusion criteria and significant deviations to subject management and protocol procedures must be documented on the appropriate eCRF. Major protocol deviations/violations will include, but are not limited to, the following:

- Did not meet any critical inclusion/exclusion criteria which may impact the assessment of treatment efficacy.
- Did not receive randomized treatment (i.e., the actual treatment is not randomized treatment).
- Use of prohibited concomitant medications (e.g., prescription or OTC anti-diarrheal drug product, NSAIDs [with the exception of acetaminophen and paracetamol] or opioid analgesics).
- Did not meet the drug compliance of taking  $\geq 7$  to  $\leq 11$  doses.
- Did not come for Visit 3 or did not provide efficacy data for 24 hour to 48 hour period after the last dose.

A list of protocol deviations will be compiled prior to database closure for the primary analysis

and be updated prior to the analysis. The deviations will be listed on randomized population and also will be summarized on randomized population by treatment group.

[figure not shown]
Further, all the protocol deviations will be manually reviewed by the medical monitor of the study to determine whether any deviation is significant with respect to per-protocol population. Such deviations which may affect the treatment evaluation would be declared as “significant” protocol deviation by the medical monitor, and consequently these subjects will also be excluded from the per-protocol population for the primary efficacy analysis, in addition to above mentioned protocol deviations.

The medical monitor will send the significant protocol deviations to Biostatistics team in an excel sheet through email before DB lock. All these significant protocol deviations will also be submitted to regulatory in the form of XPT file along with the protocol deviations captured in the eCRF. The additional list of these protocol deviations will be prepared with respect to per-protocol population criteria and will be listed on randomized population by treatment group.

### **8.7 Analysis Conventions**

The following conventions will be applied to all data presentations and analyses.

- Summary statistics will consist of the number and percentage of responses in each level for categorical variables, and the sample size (n), mean, standard deviation (SD), median, minimum and maximum values for continuous variables.
- All mean and median values will be formatted to one more decimal place than the measured value. Standard deviation values will be formatted to two more decimal places than the measured value. Minimum and maximum values will be presented with the same number of decimal places as the measured value.
- The number and percentage of responses will be presented in the form xx (xx.x) where the percentage is in the parentheses.
- All summary tables will include the analysis population sample size (i.e., number of subjects).
- Change from baseline will be calculated as follows:  
Change = (baseline value)–(post-baseline value).
- All listings will be sorted for presentation by treatment and subject.
- Date variables will be formatted as DDMMYYYY and time format is HH:MM for presentation.
- SAS Version 9.4 or higher will be the statistical software package used for all data analysis.
- A separate document with programming instructions will be prepared that will describe the derivation of these populations, before the database lock (DBL) or treatment unblinding for

the study. This document will also include specifications and programming instructions for creating analysis datasets. An analysis dataset is a dataset created to answer specific analysis purposes which will include all the variables from raw dataset, population flags, treatment flags and some derived variables as per requirement.

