9.5 Analysis of Safety Parameters

All adverse events (AEs) and treatment-emergent AEs (TEAEs) reported during the study will be summarized/reviewed in order to assess safety. Safety will be evaluated by incidence of TEAEs including incidence of selected TEAEs of special interest, incidence of SAEs; TEAEs by relationship to study drug and intensity; and TEAEs leading to discontinuation. Observed results and change from baseline in clinical laboratory tests, vital signs, and physical examinations will be tabulated by treatment group.

MedDRA (using the latest available version) will be used to classify all AEs with respect to SOC and preferred term. All safety summaries will be performed on the safety analysis set by treatment group without inferential statistics.

Total extent of exposure to study drug will be measured by total number of tablets taken and duration of exposure calculated as date of last dose minus date of first dose plus 1. Study drug compliance (%) will be calculated as number of tablets taken divided by number of tablets expected to take multiplied by 100. Subjects are considered to have good compliance if the compliance (%) is within the range of ~75% to ~125%, corresponding to 7 to 11 doses.

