#### 4.2 Safety Endpoints

The safety endpoints are:

1. Number and proportion of subjects reporting adverse events
2. Changes in clinical laboratory tests, vital signs, and physical examinations from baseline
3. Prior or Concomitant Medication
4. Medical History
5. Enteric symptoms

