### **7.6.3 Vital Signs**

Vital signs from each visit and the change from the baseline to each post-baseline visit will be summarized using descriptive statistics for the safety population. No formal inferential tests of significance will be performed. All vital signs data will be listed by treatment group and patient.

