### **7.6.4 Laboratory investigations**

Laboratory investigations of hematology, biochemistry and urine analysis tests performed for the safety population at screening (Visit I) will be repeated at TOC to ensure study subject safety and will be summarized accordingly.

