## **8. STUDY CONDUCT**

This section details general conventions to be used for the statistical analyses. Departures from these general conventions may be given in the specific detailed sections of this analysis plan.

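### SAP 8.7 defines change from baseline as baseline minus post-baseline, so laboratory and vital-sign increases would be tabulated as decreases

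*SAP*

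**What the plan says.** SAP 8.7 defines change from baseline as "Change = (baseline value)–(post-baseline value". The list that contains it opens with "The following conventions will be applied to all data presentations and analyses", so the rule is general.

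The introduction to SAP section 8 leaves room for exceptions: "Departures from these general conventions may be given in the specific detailed sections of this analysis plan". The two sections where one would be expected contain none:

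- SAP 7.6.3 (Vital Signs) says that "the change from the baseline to each post-baseline visit will be summarized using descriptive statistics".
- SAP 7.6.4 (Laboratory investigations) says only that the screening tests "will be repeated at TOC to ensure study subject safety and will be summarized accordingly".

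Change from baseline is a declared safety endpoint. SAP 4.2 lists "Changes in clinical laboratory tests, vital signs, and physical examinations from baseline", and Protocol 7.4 lists the same parameter. Protocol 9.5 requires that "Observed results and change from baseline in clinical laboratory tests, vital signs, and physical examinations will be tabulated by treatment group". The protocol gives no formula for change.

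**The concern.** A change from one time point to a later one is ordinarily the later value minus the earlier value, so that a rise is positive. The SAP formula has the terms the other way round. Neither document gives a reason for this, such as an intention to report a reduction or improvement score. Such a score would not suit measures where movement in either direction matters, for example sodium, white cell count or pulse.

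What is at stake is how the safety tables are read. The variables affected include creatinine, bilirubin, the transaminases, haemoglobin and platelets (Protocol 7.6), and blood pressure, pulse and temperature (Protocol 7.7). If the programmer follows the SAP, a rise in a liver enzyme or creatinine carries a minus sign under a change-from-baseline heading, and a fall in haemoglobin carries a plus sign. Safety is summarised descriptively, so no test result would bring the reversal to light.

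**Working it through.** The plan states no figure to reproduce. The check is a reading of the formula followed by sign arithmetic.

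**Which rule governs.** SAP 8.7 is general, and section 8 allows departures only where a specific section gives one. SAP 7.6.3 and 7.6.4 give none, so the 8.7 formula applies to both vital signs and laboratory data. The line is in the current body of the SAP, not its revision history. Both terms are named, and nothing around the formula is blacked out.

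**What the rule does.** Let B be the baseline value and P the post-baseline value.

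- SAP 8.7: D_SAP = B - P
- Usual definition, and the ordinary reading of SAP 7.6.3: D = P - B
- Therefore D_SAP = -D for every subject, variable and visit.

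**Illustration (assumed values, not trial data).**

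| Variable | Baseline | TOC | SAP 8.7 (B - P) | Usual (P - B) |
|---|---|---|---|---|
| ALT, U/L | 30 | 70 | 30 - 70 = -40 | 70 - 30 = +40 |
| Haemoglobin, g/dL | 14 | 12 | 14 - 12 = +2 | 12 - 14 = -2 |

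**Effect on the summary statistics named in SAP 8.7.**

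- Mean and median: sign reversed.
- Minimum: becomes minus the usual maximum.
- Maximum: becomes minus the usual minimum.
- Standard deviation and n: unchanged.
- Differences between arms in mean change: same size, opposite sign.

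**What is not touched.** Clinical cure and microbiological cure are proportions. Time to last unformed stool has its own formula in SAP 4.1.2, which subtracts the earlier time from the later one. Categorical physical-examination findings have no numerical change.

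**The case against.** The case for leaving this as a minor editorial matter has several parts.

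- **The protocol does not contradict the formula.** Protocol 9.5 asks for change from baseline without defining its direction. This stands as far as an explicit formula goes. The conflict is with the ordinary meaning of the term and with the wording of SAP 7.6.3.
- **A disclosed convention is usable, even if unusual.** This is true only if each table states the direction. The SAP text does not require that.
- **The shells and derivation specifications might correct it.** SAP Appendices I and III place these in separate documents, which were not available for this check, so a label or correction there cannot be excluded. If they use post-baseline minus baseline, they contradict the SAP. If they follow the SAP, the tables mislead. The line needs correcting in either case.
- **The laboratory part is less direct.** SAP 7.6.4 does not mention change. This stands: for laboratory data the point rests on SAP 4.2 and Protocol 9.5.
- **Readers have safeguards.** Observed values by visit are to be tabulated as well, Protocol 9.1 foresees shift tables where appropriate, and abnormal laboratory findings can be recorded as adverse events. A careful reader could detect the reversal, but a table should not depend on that.
- **The consequences are limited.** Protocol 9.5 says "All safety summaries will be performed on the safety analysis set by treatment group without inferential statistics" and evaluates safety mainly through adverse events. All arms are reversed alike. This also stands, and it bounds the seriousness of the error.

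**Conclusion.** The formula in SAP 8.7 is wrong as written. Followed literally, it reverses the sign of every continuous laboratory and vital-sign change in all three arms, while leaving its absolute size and spread unchanged. The impact is confined to descriptive safety tables. No bioequivalence, superiority or secondary efficacy result depends on it.

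The conclusion assumes that the tables are programmed from the SAP as it stands, and that the shells and derivation specifications do not silently use the opposite sign. The line should be corrected before the tables are produced, because it affects a declared safety endpoint and the correction is almost free.

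**What to change.** In SAP 8.7, replace the formula with:

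`Change = (post-baseline value) - (baseline value)`

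Carry the same definition into the analysis-data specification and the table shells, and check that any derivation already programmed uses it. A short footnote on the change tables, stating that a positive value means an increase, would remove any remaining doubt.

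The cost is one line of SAP text under the change-control procedure in SAP section 1, plus one derivation. Data collection, sample size, error rates and efficacy analyses are unaffected.

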### APPENDIX I

**Mock Shells:** The TFL templates will be provided in a separate document.

### APPENDIX II

**PP Logic:** Specifications and logic for the derivation of per-protocol population.

### APPENDIX III

**Analysis Data Specification:** Detailed plan for derived variables (have specified attributes and definitions) to create TFLs on Subject-Level data and Basic Data Structure of domain wise analysis data will be prepared in a separated spread sheet document.
